4 DATABASE LOCK

As the analysis will be conducted in two-steps, two database locks will be done:

- First database lock (for first step analysis): will include all available data on all randomized patients up to the common cut-off date as defined in Section 3. This database lock is planned to be done approximately 4 weeks after the common cut-off date.
- Final database lock (for final analysis): will include all data of the open-label treatment period, for all patients entered in the OL period. This database lock is planned to be done approximately 4 weeks after last patient last visit.

7 LIST OF APPENDICES

Appendix A:	Potentially clinically significant abnormalities for children
Appendix B:	Potentially clinically significant abnormalities for adults
Appendix C:	Detailed statistical methodology for pattern mixture model
Appendix D:	List of MedDRA terms for CMQs
Appendix E:	Z-score calculation formula for Cogstate Battery test
Appendix F:	Cogstate normative data
Appendix G:	Effect size calculation formula for Cogstate data
Appendix H:	Pediatric formula for eGFR and creatinine clearance

Appendix A Potentially clinically significant abnormalities for children CRITERIA for POTENTIALLY CLINICALLY SIGNIFICANT ABNORMALITIES For studies in children

Parameter	Age range	PCSA	Comments
ECG parameters			Ref.: Rijnbeek P.R. et al., Eur Heart J 2001; Davignon A. et al., Ped Cardiol 1979/1980; Semizel E.et al., Cardiol Young 2008; Mulberg AE et al. Pediatric Drug Development Concepts and applications. John Wiley & sons, Inc. 2009
HR	Birth/0 to 27 days old (Neonates)	≤90 bpm and decrease from baseline ≥20 bpm ≥190 bpm and increase from baseline ≥20 bpm	
	28 days/1 month to 23 months old (Infants)	≤80 bpm and decrease from baseline $≥$ 20 bpm $≥$ 175 bpm and increase from baseline $≥$ 20 bpm	-
	24 months/2 years to <6 years old (Children)	\leq 75 bpm and decrease from baseline \geq 20 bpm \geq 140 bpm and increase from baseline \geq 20 bpm	
	6 to <12 years old (Children)	\leq 50 bpm and decrease from baseline ≥20 bpm ≥120 bpm and increase from baseline ≥20 bpm	-
	12 to 16/18 years old (Adolescents)	\leq 50 bpm and decrease from baseline ≥20 bpm ≥120 bpm and increase from baseline ≥20 bpm	-
PR	Birth/0 to 27 days old (Neonates)	≥120 ms	
	28 days/1 month to 23 months old (Infants)	≥140 ms	
	24 months/2 years to <6 years old (Children)	≥160 ms	
	6 to <12 years old (Children)	≥170 ms	-
	12 to 16/18 years old (Adolescents)	≥180 ms	

Parameter	Age range	PCSA	Comments
QRS	Birth/0 to 27 days old (Neonates)	≥85 ms	
	28 days/1 month to 23 months old (Infants)	≥85 ms	_
	2 to <6 years old (Children)	≥95 ms	_
	6 to <12 years old (Children)	≥100 ms	_
	12 to 16/18 years old (Adolescents)	≥110 ms	_
QTc	Birth/0 to <12 years old	Absolute values (ms) Borderline: 431-450 ms	To be applied to QTcF
	(Neonates,	Prolonged*: >450 ms	*QTc prolonged and
	Infants, Children)	Additional: ≥500 ms	$\Delta QTc > 60 ms are the$
		AND	PCSA to be identified in individual subjects/patients listings.
		Increase from baseline	
		Borderline: Increase from baseline 30-60 ms Prolonged*: Increase from baseline >60 ms	
	12 to 16/18 years old (Adolescents)	Borderline: 431-450 ms (Boys); 451-470 ms (Girls) Prolonged*: >450 ms (Boys); >470 ms (Girls) Additional: ≥500 ms	
		AND	
		Increase from baseline	
		Borderline: Increase from baseline 30-60 ms	
		Prolonged*: Increase from baseline >60 ms	

Parameter	Age range	PCSA	Comments
Vital Signs			Ref.: Kidney Disease Outcomes Quality Initiatives (KDOQI) Guideline 13; 1996; The fourth report on the diagnosis, evaluation, and treatment of high blood pressure in children and adolescents, Pediatrics 2004; Bowman E & Fraser S Neonatal Handbook 2012; Mulberg AE et al. Pediatric Drug Development Concepts and applications. John Wiley & sons, Inc. 2009; Pediatric respiratory rates http://www.health.ny.gov/
SBP	Birth/0 to 27 days old (Neonates)	\leq 60 mmHg and decrease from baseline ≥20 mmHg ≥85 mHg and increase from baseline ≥20 mmHg	Based on definition of Hypertension as average - SBP or DBP >95th
	28 days/1 month to 23 months old (Infants)	\leq 70 mmHg and decrease from baseline \geq 20 mmHg \geq 98 mmHg and increase from baseline \geq 20 mmHg	percentile for gender, age, and height on ≥3 occasions
	24 months/2 years to <6 years old (Children)	\leq 70 mmHg and decrease from baseline \geq 20 mmHg \geq 101 mHg and increase from baseline \geq 20 mmHg	_
	6 to <12 years old (Children)	\leq 80 mmHg and decrease from baseline \geq 20 mmHg \geq 108 mmHg and increase from baseline \geq 20 mmHg	-
	12 to 16/18 years old (Adolescents)	\leq 90 mmHg and decrease from baseline ≥20 mmHg ≥119 mmHg and increase from baseline ≥20 mmHg	
DBP	Birth/0 to 27 days old (Neonates)	\leq 34 mmHg and decrease from baseline \geq 10 mmHg \geq 50 mHg and increase from baseline \geq 10 mmHg	
	28 days/1 month to 23 months old (Infants)	\leq 34 mmHg and decrease from baseline \geq 10 mmHg \geq 54 mHg and increase from baseline \geq 10 mmHg	
	24 months/2 years to <6 years old (Children)	\leq 34 mmHg and decrease from baseline ≥10 mmHg ≥59 mHg and increase from baseline ≥10 mmHg	-
	6 to <12 years old (Children)	\leq 48 mmHg and decrease from baseline ≥10 mmHg ≥72 mHg and increase from baseline ≥10 mmHg	-

Parameter	Age range	PCSA	Comments
	12 to 16/18 years old (Adolescents)	\leq 54 mmHg and decrease from baseline ≥10 mmHg ≥78 mHg and increase from baseline ≥10 mmHg	
Orthostatic hypotension	All age ranges	SBP: St – Su \leq -20 mmHg DBP: St – Su \leq -10 mmHg	
Temperature	All age ranges	Rectal, ear or temporal artery: >100.4°F/38.0°C Oral or pacifier: >99.5°F/37.5°C Axillary or skin infrared: >99°F/37.2°C	Ear temperature not accurate below 6 months of age
Respiratory rate	Birth/0 to 27 days old (Neonates)	<30 per minutes >60 per minutes	Based on normal range
	28 days/1 month to 23 months old (Infants)	<24 per minutes >40 per minutes	
	24 months/2 years to <6 years old (Children)	<22 per minutes >34 per minutes	_
	6 to <12 years old (Children)	<18 per minutes >30 per minutes	_
	12 to 16/18 years old (Adolescents)	<12 per minutes >20 per minutes	_
Sa02	All age ranges	<95%	
Weight	All ranges	>5% weight loss from baseline	Based on identification of trends in the child's growtl with a series of visits
			WHO Multicentre Reference Study Group, 2006; Center for Disease Control. Growth chart 200

Parameter	Age range	PCSA	Comments
Clinical Chemistry			Ref Molleston JP et al. JPGN 2011; Moritz et al., Pediatrics 1999; Moritz et al., Pediatr Nephrol 2005; Sedlacek et al., Seminars in Dialysis 2006) Gong G et al. Clinical Biochemistry 2009; Masilamani et al. Arch Dis Children 2012; Mulberg AE et al. Pediatric Drug Development Concepts and applications. John Wiley & sons, Inc. 2009
ALT/SGPT	All age ranges	By distribution analysis: >3 ULN >5 ULN >10 ULN >20 ULN	Enzymes activities must be expressed in ULN, not in IU/L. Concept paper on DILI – FDA draft Guidance Oct 2007. Internal DILI WG Oct 2008. Categories are cumulative. First row is mandatory. Rows following one mentioning zero can be deleted.
AST/SGOT	All age ranges	By distribution analysis: >3 ULN >5 ULN >10 ULN >20 ULN	Enzymes activities must be expressed in ULN, not in IU/L. Concept paper on DILI – FDA draft Guidance Oct 2007. Internal DILI WG Oct 2008. Categories are cumulative. First row is mandatory. Rows following one mentioning zero can be deleted.
Alkaline Phosphatase	All age ranges	>1.5 ULN	Enzymes activities must be expressed in ULN, not in IU/L. Concept paper on DILI – FDA draft Guidance Oct 2007. Internal DILI WG Oct 2008

Property of the Sanofi Group - strictly confidential

		For studies in children	
Parameter	Age range	PCSA	Comments
Total Bilirubin	All age ranges	>1.5 ULN >2 ULN	Enzymes activities must be expressed in ULN, not in IU/L. Concept paper on DILI – FDA draft Guidance Oct 2007.
			Internal DILI WG Oct 2008.
Conjugated Bilirubin	All age ranges	>35% Total Bilirubin and TBILI>1.5 ULN	Conjugated bilirubin dosed on a case-by-case basis.
ALT and Total All Bilirubin	All age ranges	ALT >3 ULN and Total Bilirubin > 2 ULN	Concept paper on DILI – FDA draft Guidance Oct 2007. Internal DILI WG Oct 2008.
			To be counted within a same treatment phase, whatever the interval between measurement.
СРК	All age ranges	>3 ULN >10 ULN	FDA Feb 2005. Am J Cardiol April 2006. Categories are cumulative.
			First row is mandatory. Rows following one mentioning zero can be deleted.
Creatinine	Birth/0 to <6 years old (Neonates, Infants, Children)	>53 µmol/L or 0.6 mg/dL	CF = mg x 8.8 = µmol Based on normal ranges: <0.6 mo/dL (0-1 vear).
	6 years to <12 years old (Children)	≥ 90 μ mol/L or 1.1 mg/dL	0.5 to 1.5 mg/dL (1 to 16/18 years)
	12 years to 16/18 years old (Adolescents)	\geq 132 µmol/L or 1.5 mg/dL	
Creatinine Clearance	All age ranges	50% of normal	Based on GFR Bedside Schwartz Formula
			Based on normal ranges: 20 to 50 (<8 days), 25 to 80 (8 days to 1 month), 30 to 90 (1-6 months), 40 to 115 (6-12 months), 60 to 190 (12-23 months), 90 to 165 (2-12 years),

CRITERIA for POTENTIALLY CLINICALLY SIGNIFICANT ABNORMALITIES

80-120 (After 12 years)

Parameter	Age range	PCSA	Comments
Uric Acid	All age ranges	≤ 2.0 mg/dL or 119 µmol/L	CF = mg x 5.95 = µmol
		\geq 8.0 mg/dL or 476 µmol/L	Based on normal ranges: 2.4 to 6.4 mg/dL
Blood Urea Nitrogen	Birth/0 to 27 days	≥4.3 mmol/L or 12 mg/dL	CF = g x 16.66 = mmol
(BUN)	old (Neonates)		Based on normal ranges:
	28 days/1 month to 16/18 years old (Infants, Children, Adolescents)	≥6.4 mmol/L or 18 mg/dL	3 to 12 mg/dL (NN; 5 to 18 mg/dL (other classes of age)
Chloride	All age ranges	≤80 mmol/L or 80 mEq/L	CF = 1
		≥115 mmol/L or 115 mEq/L	Based on normal range: 98 to 106
Sodium	All age ranges	≤129 mmol/L or 129 mEq/L	CF = 1
		≥150 mmol/L or 150 mEq/L	Based on normal range: 134 to 146
Potassium	Birth/0 to 27 days old (Neonates)	≤3.0 mmol/L or 3.0 mEq/L	CF = 1
		≥7.0 mmol/L or 7.0 mEq/L	Based on normal ranges:
	28 days/1 month to 23 months old (Infants)	≤3.5 mmol/L or 3.5 mEq/L	3.0 to 7.0 (NN); 3.5 to 6.0 (Infants): 3.5 to
		≥6.0 mmol/L or 6.0 mEq/L	5.0 (> Infants)
	24 months/2 years	≤3.5 mmol/L or 3.5 mEq/L	
	to 16/18 years old (Children, Adolescents)	≥5.5 mmol/L or 5.5 mEq/L	
Bicarbonate	All age ranges	≤16 mmol/L or 16 mEq/L	CF = 1
		>ULN	Based on normal range: 18 to 26
Calcium total	All age ranges	≤2.0 mmol/L or 8.0 mg/dL	CF = mg x 0.025 = mmol
		≥2.9 mmol/L or 11.6 mg/dL	Based on normal range: 8.4 to 10.9 mg/dL
Calcium ionized	All age ranges	≤1.0 mmol/L or 4.0 mg/dL	CF = mg x 0.025 = mmol
		≥1.4 mmol/L or 5.6 mg/dL	Based on normal range: 4.0 to 5.1 mg/dL

Parameter	Age range	PCSA	Comments
Total Cholesterol	All age ranges	≥6.20 mmol/L or 240 mg/dL	CF = g x 2.58 = mmol Based on normal ranges: 45 to 182 mg/dL (1-3 years), 109 to 189 mg/dL (4-6 years), 126 to 191 mg/dL (Boys 6-9 years), 122 to 209 mg/dL (Girls 6-9 years), 130 to 204 mg/dL (Boys 10-14 years), 124-217 mg/dL (Girls 10-14 years), 114 to 198 mg/dL (Boys 15-19 years), 125 to 212 mg/dL (Girls 14-19 years)
Triglycerides	All age ranges	≥4.0 mmol/L or 350 mg/dL	After >12 hours of fast) $CF = g \times 1.14 = mmol$ Based on normal ranges: 30 to 86 mg/dL (Boys 0-5 years), 32 to 99 mg/dL (Girls 0-5 years), 31-108 mg/dL (Boys 6-11 years), 35 to 114 mg/dL (Girls 6-11 years), 36 to 138 mg/dL (Boys 12-15 years), 43 to 138 mg/dL (Girls 12-15 years), 40 to 163 mg/dL (Boys 16-19 years), 40-128 mg/dL (Girls 16-19 years)
Lipasemia	All age ranges	≥2 ULN	Based on normal ranges: 3 to32 U/L (1-18 years)
Amylasemia	All age ranges	≥2 ULN	Based on normal ranges: 10 to 30 U/L (NN), 10 to 45 U/L (1-18 years)
Glucose	All age ranges	Hypoglycaemia <2.7 mmol/L or 50 mg/dL	CF = g x 5.55 = mmol
		Hyperglycaemia >7 mmol/L or 120 mg/dL (fasted after >12 hours of fast); >10.0 mmol/L or 180 mg/dL (unfasted)	Based on normal ranges: 50 to 90 mg/dL (NN), 60 to 100 mg/dL (Child)
Albumin	All age ranges	≤25 g/L	

Parameter	Age range	PCSA	Comments
CRP	All age ranges	>2 ULN or >10 mg/L (if ULN not provided)	Based on normal ranges: <6 mg/L FDA Sept 2005.
Hematology			Common Terminology Criteria for Adverse Events v3.0 (CTCAE), 2006; Division of Microbiology and Infections Diseases Pediatric Toxicity Tables, 2007; Division of AIDS Table for Grading the Severity of Adult and Pediatric Adverse Events, 2004; Mulberg AE et al. Pediatric Drug Development Concepts and applications. John Wiley & sons, Inc. 2009; Family Practice Notebook, LLC, 2012; Tietz NW et al. Clinical Guide to Laboratory Testing, 3rd edition 1995
WBC	Birth/0 to 27 days old (Neonates)	<4.0 GIGA/L or 4 000/mm ³ >25.0 GIGA/L or 25 000/mm ³	To be used if no differential count available
	28 days/1 month to 23 months old (Infants)	<4.0 GIGA/L or 4 000/mm ³ >20.0 GIGA/L or 20 000/mm ³	Based on normal ranges: 9 000 to 30 000/mm ³ (birth), 9 400 to 38 000/mm ³ (0-1 day).
	24 months/2 years to <6 years old (Children)	<3.0 GIGA/L or 3 000/mm ³ >16.0 GIGA/L or 16 000/mm ³	5 000 to 21 000/mm ³ (1 day-1 month), 6 000 to 17 500/mm ³ (1 month-
	6 to <12 years old (Children)	<5.0 GIGA/L or 5 000/mm ³ >17.0 GIGA/L or 17 000/mm ³	2 years), 5 000 to 17 000/mm ³ (2-6 years), 4 500 to 15 500/mm ³
	12 to 16/18 years old (Adolescents)	<4,5 GIGA/L or 5 000/mm ³ >13.5 GIGA/L or 17 000/mm ³	(6-11 years), 4 500 to 13 500/mm³ (11-18 years)
Lymphocytes (ALC)	Birth/0 to 27 days old (Neonates)	<1.2 GIGA/L or 1 200/mm ³ >17.0 GIGA/L or 17 000/mm ³	Based on normal ranges: 2 000 to 11 500/mm ³
	28 days/1 month to 23 months old (Infants)	<2.0 GIGA/L or 2 000/mm ³ >13.5 GIGA/L or 13 500/mm ³	17 000 /mm ³ (2 days- 1 month), 3 000 to 13 500 /mm ³ (1 month-
	24 months/2 years to <6 years old (Children)	<1.0 GIGA/L or 1 000/mm ³ >9.5 GIGA/L or 9 500/mm ³	2 years), 1,500 to 9 500/mm³ (2-6 years), 1 500 to 8 000/mm³

Parameter	Age range	PCSA	Comments
	6 to <12 years old (Children)	<1.0 GIGA/L or 1 000/mm ³ >8.0 GIGA/L or 8 000/mm ³	(6-10 years), 1 200 to 5 200/mm ³ (10-18 years)
	12 to 16/18 years old (Adolescents)	<0.6 GIGA/L or 600/mm ³ >6.0 GIGA/L or 6 000/mm ³	_
Absolute Neutrophil Count (ANC)	Birth/0 to 27 days old (Neonates)	<4.0 GIGA/L or 4 000/mm ³ (1 day old) <1.5 GIGA/L or 1 500/mm ³ (2-7 days old) <1.25 GIGA/L or 1 250/mm3 (>7 day-1month old) >1 ULN	Based on normal ranges: 5 000 to 28 000 /mm ³ (0-1 day), 1 000 to 10 000 (1 day-1 month), 1 000 to 8 500
	28 days/1 month to 23 months old (Infants)	<1.0 GIGA/L or 1 000/mm ³ (1-3 months) <1.2 GIGA/L or 1 200/mm ³ (3-24 months) >1 ULN	 (1-12 months), 1 500 to 8 500 (1 to 6 years), 1 500 to 8 000 (6 to 10 years), 1 800 to
	24 months/2 years to <6 years old (Children)	<1.2 GIGA/L or 1 200/mm³ >1 ULN	8 000 (10 to 18 years)
	6 to <12 years old (Children)	<1.2 GIGA/L or 1 200/mm³ >1 ULN	
	12 to 16/18 years old (Adolescents)	<1.2 GIGA/L or 1 200/mm ³ >1 ULN	_
Eosinophils	All age ranges	>0.5 GIGA/L or 500/mm ³ Or > ULN if ULN >0.5 GIGA/L or 500/mm ³	Based on normal ranges: 0 to 500 /mm ³ (0-1 month), 0 to 300 /mm ³ (1 month- 18 years)
Hemoglobin	Birth/0 to 27 days old (Neonates)	<86 mmol/L or 12.0 g/dL or any decrease ≥0.31 mmol/L or 2 g/dL	CF = g x 1.55 = mmol Based on normal ranges:
	28 days/1 month to 23 months old (Infants)	<1.40 mmol/L or 9.0 g/dL or any decrease ≥0.31 mmol/L or 2 g/dL	15 to 20 g/dL (0-3 days), 12.5 to 18.5 g/dL (1-2 weeks), 10.0 to
	24 months/2 years to <16/18 years old (Children, Adolescents)	<1.55 mmol/L or10.0 g/dL or any decrease ≥0.31 mmol/L or 2 g/dL	 13.0 g/dL (1-0 months), 10.5 to 13.0 g/dL (7 months-2 years), 11.5 to 13.0 g/dL (2-5 years), 11.5 to 14.5 (5-8 years), 12.0 to 15.2 g/dL (13-18 years)
Hematocrit	Birth/0 to 27 days	<0.39 l/l or 40%	CF = % x 0.01 = I/I
	old (Neonates)	>0.61 l/l or 47%	Based on normal ranges: 45% to 61% (0-3 days), 39% to 57% (1-2 weeks), 29% to 42% (1-6 months),
	28 days/1 month to 23 months old (Infants)	<0.29 l/l or 29% >0.42 l/l or 42%	

Parameter	Age range	PCSA	Comments
	24 months/2 years to <12 years old (Children)	<0.32 l/l or 32% >0.47 l/l or 47%	33% to 38% (7 months- 2 years), 34% to 39% (2-5 years), 35% to 42%
	≥12 years (Adolescents)	≤0.37 I/I or 37% (Male) ≤0.32 I/I or 32% (Female) ≥0.55 I/I or 55% (Male) ≥0.5 I/I or 50% (Female)	(13-18 years); 36% to 47% (13-18 years)
Platelets	All age ranges	<100 GIGA/L or 100 000/mm ³ >700 GIGA/L or 700 000/mm ³	Based on normal ranges: 250 000 to 450 000/mm ³ (NN); 300 000 to 700 000/mm ³ (1-6 months), 250 000 to 600 00/mm ³ (7 months- 2 years), 250 000 to 550 000/mm ³ (2-12 years), 150 000 to 450 000/mm ³ (13-18 years)
Urinalysis			Patel HP, Pediatr Clin N Am, 2006
Ketonuria	All age ranges	Presence	Semi-quantitative methods
Glycosuria	All age ranges	Presence	Semi-quantitative methods
Hematuria	All age ranges	≥1+	Semi-quantitative methods
Proteinuria	All age ranges	≥1+	Semi-quantitative methods
End of Document			

Appendix B Potentially clinically significant abnormalities for adults

CRITERIA for POTENTIALLY CLINICALLY SIGNIFICANT ABNORMALITIES for phase 2/3 studies (oncology excepted)

Parameter	PCSA	Comments			
Clinical Chemistry					
ALT	By distribution analysis : >3 ULN	Enzymes activities must be expressed in ULN, not in IU/L.			
	>5 ULN >10 ULN	Concept paper on DILI – FDA draft Guidance Oct 2007. Internal DILI WG Oct 2008.			
	>20 ULN	Categories are cumulative. First row is mandatory. Rows following one mentioning zero can be deleted.			
AST	By distribution analysis : >3 ULN	Enzymes activities must be expressed in ULN, not in IU/L.			
	>5 ULN >10 ULN	Concept paper on DILI – FDA draft Guidance Oct 2007. Internal DILI WG Oct 2008.			
	>20 ULN	Categories are cumulative. First row is mandatory. Rows following one mentioning zero can be deleted.			
Alkaline Phosphatase	>1.5 ULN	Enzymes activities must be expressed in ULN, not in IU/L. Concept paper on DILI – FDA draft Guidance Oct 2007. Internal DILI WG Oct 2008.			
Total Bilirubin	>1.5 ULN >2 ULN	Must be expressed in ULN, not in µmol/L or mg/L. Categories are cumulative. Concept paper on DILI – FDA draft Guidance Oct 2007. Internal DILI WG Oct 2008.			
Conjugated Biliru	bin >35% Total Bilirubin and TBILI>1.5 ULN	Conjugated bilirubin dosed on a case-by-case basis.			
ALT and Total Bilirubin	ALT>3 ULN and TBILI>2 ULN	Concept paper on DILI – FDA draft Guidance Oct 2007. Internal DILI WG Oct 2008. To be counted within a same treatment phase, whatever the interval between measurement.			
СРК	>3 ULN >10 ULN	FDA Feb 2005. Am J Cardiol April 2006. Categories are cumulative. First row is mandatory. Rows following one mentioning zero can be deleted.			

Parameter	PCSA	Comments
CLcr (mL/min) (Estimated creatinine clearance based on the Cokcroft-Gault equation)	<15 (end stage renal disease) ≥15 - <30 (severe decrease in GFR) ≥30 - < 60 (moderate decrease in GFR) ≥60 - <90 (mild decrease in GFR) ≥ 90 (normal GFR)	FDA draft Guidance 2010 Pharmacokinetics in patients with impaired renal function-study design, data analysis, and impact on dosing and labeling
eGFR (mL/min/1.73m2) (Estimate of GFR based on an MDRD equation)	<15 (end stage renal disease) ≥15 - <30 (severe decrease in GFR) ≥30 - < 60 (moderate decrease in GFR) ≥60 - <90 (mild decrease in GFR) ≥ 90 (normal GFR)	FDA draft Guidance 2010 Pharmacokinetics in patients with impaired renal function-study design, data analysis, and impact on dosing and labeling
Creatinine	≥150 µmol/L (Adults) ≥30% change from baseline ≥100% change from baseline	Benichou C., 1994.
Uric Acid Hyperuricemia Hypouricemia	>408 μmol/L <120 μmol/L	Harrison- Principles of internal Medicine 17th Ed., 2008.
Blood Urea Nitroge	n ≥17 mmol/L	
Chloride	<80 mmol/L >115 mmol/L	
Sodium	≤129 mmol/L ≥160 mmol/L	
Potassium	<3 mmol/L ≥5.5 mmol/L	FDA Feb 2005.
Total Cholesterol	≥7.74 mmol/L	Threshold for therapeutic intervention.
Triglycerides	≥4.6 mmol/L	Threshold for therapeutic intervention.
Lipasemia	≥3 ULN	
Amylasemia	≥3 ULN	
Glucose Hypoglycaemia Hyperglycaemia	≤3.9 mmol/L and <lln ≥11.1 mmol/L (unfasted); ≥7 mmol/L (fasted)</lln 	ADA May 2005. ADA Jan 2008.
HbA1c	>8%	
Albumin	≤25 g/L	

Property of the Sanofi Group - strictly confidential

Parameter PCSA		Comments	
CRP	>2 ULN or >10 mg/L (if ULN not provided)	FDA Sept 2005.	
Hematology			
WBC	<3.0 Giga/L (Non-Black); <2.0 Giga/L (Black) ≥16.0 Giga/L	Increase in WBC: not relevant. To be interpreted only if no differential count available.	
Lymphocytes	>4.0 Giga/L		
Neutrophils	<1.5 Giga/L (Non-Black);<1.0 Giga/L (Black)	International Consensus meeting on drug-induced blood cytopenias, 1991. FDA criteria.	
Monocytes	>0.7 Giga/L		
Basophils	>0.1 Giga/L		
Eosinophils	>0.5 Giga/L or >ULN (if ULN≥0.5 Giga/L)	Harrison- Principles of internal Medicine 17th Ed., 2008.	
Hemoglobin	≤115 g/L (Male); ≤95 g/L (Female) ≥185 g/L (Male); ≥165 g/L (Female)	Criteria based upon decrease from baseline are more relevant than based on absolute value. Other categories for decrease from baseline can be used	
	Decrease from Baseline ≥20 g/L	(≥30 g/L, ≥40 g/L, ≥50 g/L).	
Hematocrit	≤0.37 v/v (Male) ; ≤0.32 v/v (Female) ≥0.55 v/v (Male) ; ≥0.5 v/v (Female)		
RBC	≥6 Tera/L	Unless specifically required for particular drug development, the analysis is redundant with that of Hb. Otherwise, consider FDA criteria.	
Platelets	<100 Giga/L ≥700 Giga/L	International Consensus meeting on drug-induced blood cytopenias, 1991.	
Urinalysis			
рН	≤4.6 ≥8		
Vital signs			
HR	≤50 bpm and decrease from baseline ≥20 bpm ≥120 bpm and increase from baseline≥20 bpm	To be applied for all positions (including missing) except STANDING.	
SBP	≤95 mmHg and decrease from baseline ≥20mmHg ≥160 mmHg and increase from baseline ≥20 mmHg	To be applied for all positions (including missing) except STANDING.	

Parameter	PCSA	Comments To be applied for all positions (including missing) except STANDING.	
DBP	≤45 mmHg and decrease from baseline ≥10 mmHg ≥110 mmHg and increase from baseline ≥10 mmHg		
Orthostatic Hypotension Orthostatic SDB Orthostatic DBP	≤-20 mmHg ≤-10 mmHg		
Weight	≥5% increase from baseline ≥5% decrease from baseline	FDA Feb 2007.	
ECG		Ref.: ICH E14 guidance (2005) and E14 Q&A (2012), and Cardiac Safety Research Consortium White Paper on PR and QRS (Nada et al. Am Heart J. 2013; 165(4) : 489-500)	
HR	<50 bpm <50 bpm and decrease from baseline ≥20 bpm <40 bpm <40 bpm and decrease from baseline ≥20 bpm <30 bpm <30 bpm and decrease from baseline ≥20 bpm	Categories are cumulative	
	>90 bpm >90 bpm and increase from baseline ≥20bpm >100 bpm >100 bpm and increase from baseline ≥20bpm >120 bpm >120 bpm and increase from baseline ≥20 bpm	Categories are cumulative	
PR	 >200 ms >200 ms and increase from baseline ≥25% > 220 ms > 220 ms and increase from baseline ≥25% > 240 ms > 240 ms and increase from baseline ≥25% 	Categories are cumulative	
QRS	 >110 ms >110 msec and increase from baseline ≥25% >120 ms >120 ms and increase from baseline ≥25% 	Categories are cumulative	
QT	>500 ms		

Property of the Sanofi Group - strictly confidential

Parameter	PCSA	Comments
QTc	Absolute values (ms)	To be applied to any kind of QT correction formula. Absolute values categories are cumulative
	>450 ms >480 ms >500 ms	QTc >480 ms and Δ QTc>60 ms are the 2 PCSA categories to be identified in individual subjects/patients listings.
	Increase from baseline Increase from baseline]30-60] ms Increase from baseline >60 ms	

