2.4.5 Analyses of safety data

No formal inferential testing will be performed for either study period. Summaries will be descriptive in nature. All summaries of safety results described below will be presented for each study period respectively, unless otherwise noted.

General common rules

All safety analyses will be performed on the safety population for the double-blind period and on the OL population for the OL period, as defined in Section 2.3.2 unless otherwise specified, using the following common rules:

- Safety data in patients who do not belong to the safety population (ie, exposed but not randomized) will be listed separately.
- The baseline value for both double-blind and OL periods is defined as the last available value obtained up to the date and time of the first double-blind IMP injection in EFC14643 study, except otherwise specified.
- PCSA values are defined as abnormal values considered medically important by the Sponsor according to predefined criteria/thresholds based on literature review and defined by the Sponsor for clinical laboratory tests and vital signs, PCSA in children [Appendix A] and PCSA in adults version dated May 2014 [Appendix B]). Considering that the threshold defined in the PCSA list for monocytes and basophils can be below the ULN, the following PCSA criteria will be used for the PCSA analysis of monocytes and basophils:
 - PCSA criterion for monocytes: >0.7 Giga/L or > ULN (if ULN ≥ 0.7 Giga/L)
 - PCSA criterion for basophils: >0.1 Giga/L or > ULN (if ULN \ge 0.1 Giga/L)
- PCSA criteria will determine which patients had at least 1 PCSA during the TEAE period, taking into account all evaluations performed during the TEAE period, including nonscheduled or repeated evaluations.
- The treatment-emergent PCSA denominator by group for a given parameter will be based on the number of patients assessed for that given parameter at least once during the TEAE period.
- All measurements, scheduled or unscheduled, fasting or not fasting, will be assigned to analysis windows defined in Section 2.5.4, Table 5 and Table 6 in order to provide an assessment for Week 4 to Week 104 time points.

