2.4.5.3 Analyses of laboratory variables

The summary statistics (including number, mean, median, Q1, Q3, SD, minimum and maximum) of all laboratory variables (central laboratory values and changes from baseline) will be calculated for each visit or study assessment (baseline, each post-baseline value of the treatment period, last on-treatment and worst on-treatment value). In addition, for some parameters of interest, mean changes from baseline with the corresponding SE could be plotted over time (at same time points). This section will be organized by biological function as specified in Section 2.1.4.3. For glucose, only fasting samples will be summarized.

The incidence of PCSAs (list provided in Appendix A and Appendix B), as well as ALT increase as defined as AESI, at any time during the TEAE period will be summarized by biological function irrespective of the baseline level and/or according to the following baseline status categories:

- Normal/missing
- Abnormal according to PCSA criterion or criteria

For laboratory parameters for which PCSA criterion is not defined, similar table(s) using the normal range could be provided.

For clinical laboratory parameters during the OL period, summary tables as described for the double-blind period above will be used with the exceptions of the analyses by visit (unless data warrants further investigation)

Drug-induced liver injury

The liver function tests, namely AST, ALT, ALP, and total bilirubin, are used to assess possible drug-induced liver toxicity. The proportion of patients with PCSA values or ALT increase as defined in the section grouping of adverse events (see Section 2.1.4.1) during TEAE period by baseline status will be displayed for each parameter.

An evaluation of drug-induced serious hepatotoxicity (eDISH) with the graph of distribution of peak values of ALT versus peak values of total bilirubin will also be presented using post-baseline values during TEAE period. Note that the ALT and total bilirubin values are presented on a logarithmic scale. The graph will be divided into 4 quadrants with a vertical line corresponding to 3 x ULN for ALT and a horizontal line corresponding to 2 x ULN for total bilirubin.

Listing of possible Hy's law cases identified by treatment group (ie, patients with any elevated ALT>3 x ULN, and associated with an increase in bilirubin >2 x ULN, concomitantly or not) with ALT, AST, ALP, total bilirubin, and if available direct and indirect bilirubin will be provided.

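### Read by their titles, the SAP's abnormality lists give patients under 18 no change-from-baseline flag for serum creatinine, so some doublings go uncounted

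*SAP*

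**What the plan says.** SAP 2.4.5 names both lists, the children's in Appendix A and the adults' in Appendix B. SAP 2.4.5.3 plans the laboratory summary from both: "The incidence of PCSAs (list provided in Appendix A and Appendix B". Neither section gives an age rule that assigns a patient to one list.

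The creatinine rows differ in kind.

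- **Appendix A.** The limits are absolute: at least "90 μ mol/L or 1.1 mg/dL" at 6 to <12 years and at least "132 µmol/L or 1.5 mg/dL" at 12 to 16/18 years. There is no baseline condition. The comment column gives the conversion "CF = mg x 8.8 = µmol" and a normal range of 0.5 to 1.5 mg/dL for ages 1 to 16/18.
- **Appendix B.** An absolute limit of 150 µmol/L, marked for adults, is followed by "≥30% change from baseline ≥100% change from baseline". No direction is stated, although a change of 100% or more can in practice only be a rise.

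Appendix A also flags creatinine clearance at half of normal. Its comment cites the Bedside Schwartz formula and normal ranges of 90 to 165 (2-12 years) and 80 to 120 (after 12). SAP 2.5.1 instead derives clearance from the modified Schwartz equation in Appendix H.

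Eligibility is 8 to 17 years at consent (Protocol 7.2.1).

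**The concern.** The PCSA table is where the number of patients with a marked laboratory change is set side by side for alirocumab and placebo. A fixed limit near or at the top of a wide normal range is insensitive when the patient starts low in that range. The same SAP holds a criterion that works from the patient's own starting value, but places it in a list whose title excludes nearly everyone in this trial.

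The other planned outputs do not replace that count:

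- Group summaries of change and worst value show extremes, not how many patients had them.
- The normal-range table in SAP 2.4.5.3 is optional and meant for parameters without a PCSA criterion; creatinine has one.
- Under Protocol Appendix H, a creatinine rise is an adverse event only if it meets a criterion in Protocol 10.4.3, so a silent doubling need not appear.

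Protocol 11.1 raised the sample from 90 to 150 specifically to assess paediatric safety, so sensitivity of the safety tables matters here.

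**Working it through.** **1. Reproduce the printed limits.** The SAP's factor makes 1 mg/dL equal to 88 µmol/L.

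- 1.5 × 88 = 132.0, which matches.
- 1.1 × 88 = 96.8, against the printed 90. These disagree by 7.6% (96.8/90 = 1.076). SAP 2.1.4.3 reports tables in international units, so 90 is used below.
- Normal range: 0.5 × 88 = 44 to 1.5 × 88 = 132 µmol/L. The adolescent limit is the top of the normal range.

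**2. When does a doubling stay under the limit?** When baseline < limit/2.

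- 6 to <12 years: 90/2 = 45 µmol/L (96.8/2 = 48.4 if the mg/dL figure is used). Example: 44 doubles to 88, not flagged.
- 12 years and over: 132/2 = 66 µmol/L. Example: 60 doubles to 120, not flagged. From 44, a threefold rise is needed (132/44 = 3.0).

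A 30% rise stays under the limit below 90/1.3 = 69 and 132/1.3 = 102 µmol/L.

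**3. How common might such baselines be?** The documents give no baseline creatinine. Assuming 30 to 60 µmol/L at 8-11 years, the limit is reached at 90/30 = 3.0 down to 90/60 = 1.5 times baseline. Assuming 45 to 90 at 12-17, it is reached at 132/45 = 2.9 down to 132/90 = 1.5 times.

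**4. Does the clearance row catch what creatinine misses?** Clearance = k × height / (µmol/L × 0.01131). The coefficient k is 0.413 for Bedside Schwartz (Protocol Appendix I), or 0.55, with 0.70 for males 13-21 (SAP Appendix H). Half the lower and upper normal limits are 45 and 82.5 (2-12 years), and 40 and 60 (after 12). Heights are assumed.

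| Doubling | Height | k | Clearance after | Half lower limit | Half upper limit |
|---|---|---|---|---|---|
| 44 to 88, age 10 | 135 cm | 0.413 | 56.0 | missed | caught |
| 44 to 88, age 10 | 135 cm | 0.55 | 74.6 | missed | caught |
| 35 to 70, age 10 | 135 cm | 0.55 | 93.8 | missed | missed |
| 60 to 120, age 14 | 165 cm | 0.413 | 50.2 | missed | caught |
| 60 to 120, age 14 | 165 cm | 0.55 | 66.9 | missed | missed |
| 60 to 120, boy of 14 | 165 cm | 0.70 | 85.1 | missed | missed |
| 44 to 88, age 14 | 165 cm | 0.413 | 68.5 | missed | missed |

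On the lower-limit reading the misses hardly depend on height. At 88 µmol/L in a child, clearance stays above 45 for any height over 108 cm even with k = 0.413 (45 × 88 × 0.01131 / 0.413 = 108.4).

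**The case against.** **The SAP never says Appendix A alone governs minors.** This stands. Both lists are cited without an age rule, and Appendix B seems to serve some parameters for trial patients: SAP 2.4.5 rewrites the monocyte and basophil criteria, whose rows stand only in Appendix B. In the creatinine row, the adult label is attached to the 150 µmol/L limit and not to the relative lines. If Appendix B supplemented Appendix A for everyone, the gap would vanish, though two different absolute creatinine limits would then apply to the same patient. A reader might infer that a doubling is certainly flagged at 18 and certainly not at 15. The titles point that way, but the text does not establish it.

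**The clearance row is a second net.** In part. A reader might infer that it always misses a doubling; it does not. With the Bedside coefficient and half the upper limit, it catches many. It cannot be relied on, because neither the meaning of normal nor a single formula is fixed.

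**The window is narrow for children.** Also fair. A reader might infer that the table cannot count a doubling in the youngest patients. It can, from a baseline of 45 µmol/L. Within the SAP's printed normal range, the child window is only 44 to <45 µmol/L (to <48.4 by the mg/dL figure); it widens only if baselines lie below that range. The adolescent window, 44 to <66, is substantial.

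**Other safeguards exist, and renal harm is not a named risk.** Urea nitrogen has its own flag (6.4 mmol/L), urinalysis findings are tabulated, change and worst values are summarised, and no renal event is of special interest. These reduce the stakes, but none counts patients by their own creatinine rise.

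**Conclusion.** The point holds as a cheap improvement to a descriptive safety table. If the lists apply as their titles say, a doubling of creatinine is not flagged on creatinine below a baseline of 45 µmol/L at 6 to <12 years or 66 µmol/L from 12. Those cut-offs follow from the SAP's printed limits alone. How many trial patients fall below them rests on assumed baselines, and what the clearance row would catch rests on assumed heights and an unresolved definition.

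It does not follow that renal safety goes unmonitored. The PCSA list governs reporting; the protocol's follow-up chart for raised creatinine is a separate matter and is not shown in the text available. Primary efficacy is not affected.

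**What to change.** In Appendix A, creatinine row, all ages:

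- Add an increase from baseline of at least 100%, tabulated by treatment group in the double-blind and open-label periods.
- Add an increase of at least 30% for the 24-week placebo-controlled comparison only. Note beside it that growth, and small absolute changes at low baselines, can trigger it (30 to 39 µmol/L is a 30% rise). Write increase, since Appendix B says only change.

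In the same edit:

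- State which PCSA list applies to which patients, including those who turn 18 during the study.
- Define half of normal in the clearance row and name one formula, reconciling Appendix A with SAP 2.5.1 and Appendix H.
- Reconcile 90 µmol/L with 1.1 mg/dL.

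No new data are needed: Protocol 1.3 already schedules chemistry at screening and Weeks 12, 24, 32, 44, 68 and 104. Appendix A already uses change from baseline for hemoglobin, heart rate, blood pressure and weight, so the form is familiar. The cost is two table rows and some non-specific flags at 30%.
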